4.3 Schedule of Assessments

Every effort should be made to conduct the study visits as planned. Concerns related to the Coronavirus disease 2019 (COVID-19) pandemic, other natural catastrophes (e.g., hurricane), and any additional case-by-case situations may be discussed for approval with the Sponsor. Following approval, provisions may be implemented to minimize potential hazards to study subjects and to maintain compliance with local government and institutional guidance (e.g., study center has a policy that a clinical research visit must be delayed). These provisions may allow alternatives to in-person study visits and include, but are not limited to, the following: conducting remote study visits via phone/telemedicine video, focusing on safety assessments during remote visits, or performing safety labs via local laboratory or professional in-home phlebotomy vendors. Any potential issues should be discussed with Sponsor/CRO and will be addressed on an individualized basis. The Screening, Pre-Baseline Evaluation, Baseline, and Follow-up Week 8 Safety visits must be done in person. Other visits may be conducted under the provisions mentioned above (remote via phone/telemedicine, local labs, etc.).

Table 1 Schedule of Assessments

Procedure	Screening Phase (3-14 days)¹	Open-label Treatment Phase^{2,3}				Follow-up Phase²
	Screening Visit	Baseline Visit (Day 1)	Week 2 (Day 14 +/- 2 days)	Week 4 (Day 28), Week 8 (Day 56), Week 12 (Day 84), Week 16 (Day 112), & Week 20 (Day 140) (all visits +/- 2 days)	Week 24 (Day 168) (+/- 2 days) or EOT Visit	FU Week 2 and FU Week 8 Visits (both visits +/- 2 days) for all subjects⁴
Eligibility Assessments						
Informed Consent	X					
Duplicate Subject Check (in CTSdatabase)	X					
Inclusion/Exclusion Criteria	X	X				
Medical History	X					
Migraine History (signs/symptoms/prior treatment/frequency/intensity)	X					
Concomitant medication paper diary ⁵	X	X	X	X	X	X ⁵
Enroll subject / IWRS ⁶		X				
Safety Assessments						
Physical Examination ⁷	X			X (Week 12 Only)	X	
Vital Signs / Physical Measurements ⁸	X	X	X	X	X	X
Clinical Safety Laboratory Testing ⁹	X		X	X (Weeks 4, 8, 12, 16 Only)	X	
Liver Function Test (LFTs) ⁹	X	X	X	X	X	X
Lipid Panel ⁹		X		X (Week 12 only)	X	

Table 1 Schedule of Assessments

Procedure	Screening Phase (3-14 days) ¹	Open-label Treatment Phase ^{2,3}				Follow-up Phase ²

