6.2.3.1 Subject Disposition From Enrollment to Treatment

The frequency table of subject disposition from enrollment to treatment is provided for the enrolled analysis set based on the Treatment Phase Subject Status CRF, and displays the following categories:

- Treated with rimegepant (identified as subjects with nonmissing study drug start date)

- Not treated with rimegepant (identified as subjects with missing study drug start date)
 - Reasons for early discontinuation (i.e., not completing the study), including not reported. For subjects whose reason is screen failure due to inclusion/exclusion criteria, the reasons for screen failure from the Inclusion/Exclusion Criteria CRF are also included as subcategories.

6.2.3.2 *Subject Disposition During the OLT Phase*

The frequency table of subject disposition during the OLT Phase is provided for the safety analysis set based on the Treatment Phase Subject Status CRF, and displays the following categories:

- Ongoing in the OLT Phase. These are identified as subjects with (1) missing response to the question “Did the subject complete the OLT Phase?” and (2) missing study drug last date. This category only exists before LSLV database lock. After LSLV database lock, subjects with missing response are categorized as “Did not complete the OLT Phase”.
- Completed the OLT Phase. These are identified as subjects with (1) “yes” response to the question “Did the subject complete the OLT Phase?” and (2) nonmissing study drug last date.
- Did not complete the OLT Phase. These are identified as subjects with (1) “no” or missing response to the question “Did the subject complete the OLT Phase?” and (2) nonmissing study drug last date.
 - Reasons for not completing the OLT Phase, including not reported
- Continued to the Follow-Up Phase. These are identified as subjects with “yes” response to the question “Is the subject continuing to the Follow-Up Phase?”.
- Did not continue to the Follow-Up Phase. These are identified as subjects with “no” or missing response to the question “Is the subject continuing to the Follow-Up Phase?”.
 - Reasons for not continuing to the Follow-Up Phase, including not reported.

6.2.3.3 *Subject Disposition During the Follow-Up Phase*

The frequency table of subject disposition during the Follow-Up Phase is provided for the follow-up safety analysis set based on the Follow-Up Subject Status CRF, and displays the following categories:

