Study drug is rimegepant 75 mg ODT daily. Study drug is dispensed in a wallet-type blister card with a unique wallet ID. Each wallet has 8 tablets. Sites report the wallet ID, study medication start date, study medication end date, and number of tablets taken per day on the IP Dosing CRF.

The table of rimegepant exposure is provided for the safety analysis set, and summarizes the following parameters descriptively as continuous or categorical variables:

- Time on rimegepant (weeks), derived as (study drug end date – study drug start date + 1)/7
- Time on rimegepant (weeks) categories: < 2, ≥ 2 to < 4, ≥ 4 to < 8, ≥ 8 to < 12, ≥ 12 to < 16, ≥ 16 to < 20, ≥ 20 to < 24, ≥ 24

- Time on rimegepant milestone categories:
 - ≥ 3 months, defined as ≥ 11 weeks
 - ≥ 6 months, defined as ≥ 23 weeks
- Cumulative rimegepant exposure (mg), derived by summing $\{\text{number of days} \times \text{number of tablets taken per day} \times 75\}$ across records with complete study medication start dates.
 - Number of days for a record is derived as imputed study medication end date – study medication start date + 1.
- Average rimegepant exposure (mg per day), derived as cumulative rimegepant exposure/time on rimegepant (days)
- Total rimegepant exposure (mg) summed across all subjects, derived by summing cumulative exposure across all subjects
- Total rimegepant exposure (patient-years), derived by summing (study drug end date – study drug start date + 1)/365.25 across all subjects.

See Section 7.1 for derived dates.

The by-subject listing of study drug is provided for the safety analysis set based on the IP Dosing CRF, and displays wallet ID, study medication start date, study medication end date, study day derived from study medication start date, and number of tablets taken per day ≥ 0 . The listing also displays study drug start and end dates and rimegepant exposure parameters (time on rimegepant, cumulative rimegepant exposure, and average rimegepant exposure), and identifies invalid wallet IDs. Valid wallet IDs are those that are in the kit list file. The listing is sorted by site-subject ID, study medication start date, wallet ID, and study medication end date.

6.2.6.2 *Measurements of Treatment Compliance*

The frequency table of treatment compliance is provided for the safety analysis set, and displays the following categories:

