- Tablet count compliance $\geq 80\%$ from rimegepant start to later of last scheduled OLT Phase visit or rimegepant end. Tablet count compliance is derived as $100 \times$ actual cumulative tablet count/required cumulative tablet count, where
 - Actual cumulative tablet count is derived by summing the $\{\text{number of days} \times \text{number of tablets taken per day}\}$ across records with complete study medication start dates.
 - Number of days for a record is derived as imputed study medication end date – study medication start date + 1.
 - Required cumulative tablet count is derived as $\{\text{maxdate} - \text{study drug start date} + 1\}$, where maxdate is defined as the latest of the (1) scheduled Week 2, 4, 8, 12, 16, 20, and Week 24/EOT visit dates, and (2) study drug end date.
 - Scheduled visits are identified from visit labels, and therefore exclude those containing “unscheduled” in the visit label.

- If the required cumulative tablet count is < 14, then it is reset to {study drug end date – study drug start date + 1} to account for early OLT Phase termination due to baseline laboratory test exclusion criteria.
- > 1 tablet taken on any 1 day. This is determined from either of the following:
 - Records with complete study medication start date and number of tablets taken per day > 1
 - Overlapping records (see Section 9.2)
- Time on rimegepant > 26 weeks.

Results for all categories are displayed, even those with 0 counts.

The by-subject listing of treatment compliance is provided for the safety analysis set, and displays results for compliance parameters in separate columns: percentage for tablet count compliance; flags for the other parameters (“Y” or missing).

6.2.6.3 *Nonstudy Concomitant Medications*

Frequency tables of the following nonstudy concomitant medications are provided by therapeutic class and preferred name for the safety analysis set: all; acute migraine; prophylactic migraine.

Medications are displayed in descending order of overall frequency within therapeutic class and preferred name.

The by-subject listing of nonstudy medications is provided by therapeutic class and preferred name for the enrolled analysis set. Acute migraine and prophylactic migraine medications are identified.

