9 APPENDICES

9.1 Relevant Protocol Deviations

Relevant eligibility protocol deviations include the following categories:

- Treated with study drug under > 1 subject identifier. These subjects are identified from the Protocol Deviations CRF.
- Finding out of range, defined any as any of the following subcategories:
 - Females with a positive pregnancy test during pretreatment (see Section 6.4.2)
 - Estimated glomerular filtration rate (eGFR) according to the re-expressed abbreviated (4-variable) Modification of Diet in Renal Disease (MDRD) Study equation ≤ 40

mL/min/1.73m² during pretreatment, if originally consented to Protocol Version 5 or lower *

- eGFR according to the re-expressed abbreviated (4-variable) MDRD Study equation < 30 mL/min/1.73m² during pretreatment, if originally consented to Protocol Version 6 or higher *
- BMI \geq 33 kg/m² during pretreatment, if originally consented to Protocol Version 5 or lower *
- BMI $>$ 35 kg/m² during pretreatment, if originally consented to Protocol Version 6 or higher *
- C-SSRS suicidal ideation with active intent or plan to act, or suicidal behavior present during pretreatment. Defined as having a “yes” response to any of the following C-SSRS questions during pretreatment:
 - Suicidal ideation question 4 (active suicidal ideation with some intent to act, without specific) or 5 (active suicidal ideation with specific plan and intent)
 - Suicidal behavior question 1 (actual attempt), 3 (interrupted attempt), 4 (aborted attempt), 5 (preparatory acts or behavior), or 6 (suicidal behavior).

For the subcategories marked with “*”, all nonmissing values during the pretreatment analysis period must meet the deviation criteria in order to be considered a deviation.

Relevant subject management protocol deviations include the following categories:

- Study drug dosing noncompliance, defined as any of the following subcategories (see Section 6.2.6.2):
 - Tablet count compliance < 80% from rimegepant start to later of last scheduled OLT Phase visit or rimegepant end
 - > 1 tablet taken on any 1 day.
- Prohibited nonstudy medications, defined as any of the following subcategories:
 - Atypical antipsychotic, divalproex, valproic acid, or valproate taken on or after informed consent #
 - Butterbur root or extract taken up to 14 days before study drug start or afterward
 - Calcitonin gene-related peptide (CGRP) antagonist monoclonal antibody or small molecule taken on or after informed consent #

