9.2 Study Drug Dosing Day

A study drug dosing day is defined as a day on which ≥ 1 tablet of study drug was taken.

For each subject, study drug dosing days (i.e., number of tablets per day) are determined for every day in the interval defined from the study drug start date to the study drug end date inclusive.

First, study medication records with complete study medication start date and number of tablets taken per day > 0 are selected. Imputed study medication end date, study drug start date, and study drug end date are derived (see Section 7.1).

Next, records are sorted by study medication start date, imputed study medication end date, wallet ID, and number of tablets taken per day.

Let [study medication start date1, imputed study medication end date1] and [study medication start date2, imputed study medication end date2] denote any 2 records.

Overlapping records are defined as $\max(\text{study medication start date1}; \text{study medication start date2}) \leq \min(\text{imputed study medication end date1}; \text{imputed study medication end date2})$. All days from the maximum to the minimum inclusive are considered overlapping study drug dosing days on which the number of tablets taken per day > 1 . Note that overlapping records need not be consecutive.

Gaps between 2 consecutive records are defined as $\text{study medication start date2} - \text{imputed study medication end date1} \geq 2$ days. All days from the imputed study drug end date1 + 1 day to the study medication start date2 – 1 day inclusive are considered days on which no study drug was taken (i.e., not study drug dosing days).

Example:

Suppose study medication data are as follows for a given subject:

Study Medication Start Date	Study Medication End Date	Imputed Study Medication End Date	Number of Tablets Taken per Day	Note
01JAN2022	03JAN2022	03JAN2022	1	
04JAN2022	05JAN2022	05JAN2022	0	Excluded from analysis
06JAN2022	09JAN2022	09JAN2022	1	
09JAN2022	11JAN2022	11JAN2022	2	1-day overlap with previous record
13JAN2022		13JAN2022	1	1-day gap between previous record

Then study drug start date = 01JAN2022 and study drug end date = 13JAN2022.

Study drug dosing days and number of tablets per day are derived as follows for the subject, taking overlaps and gaps into account:

Date	Number of Tablets per Day	Study Drug Dosing Day Flag
01JAN2022	1	Y
02JAN2022	1	Y
03JAN2022	1	Y
04JAN2022	0	
05JAN2022	0	
06JAN2022	1	Y
07JAN2022	1	Y
08JAN2022	1	Y
09JAN2022	3	Y
10JAN2022	2	Y
11JAN2022	2	Y

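### The compliance reset meant for baseline-laboratory terminations is triggered only by a required count below 14, so some of these subjects are still labelled dosing noncompliant; tablets are also not capped at one per day

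*SAP*

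**What the plan says.** SAP 6.2.6.2 defines tablet count compliance as 100 × actual tablets / required tablets.

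- **Required count.** This runs from the study drug start date to maxdate, inclusive: "maxdate is defined as the latest of the (1) scheduled Week 2, 4, 8, 12, 16, 20, and Week 24/EOT visit dates", or the study drug end date if that is later. "Scheduled visits are identified from visit labels, and therefore exclude those containing" unscheduled ones.
- **Reset.** If the required count is below 14, it is replaced by the days from first to last dose, "to account for early OLT Phase termination due to baseline laboratory test exclusion criteria". No reason for stopping is tested.
- **Actual count.** This sums days × tablets per day over the dosing records, with no maximum of one per day.
- **Consequence.** SAP 9.1 lists "Tablet count compliance < 80% from rimegepant start to later of last scheduled OLT Phase visit or rimegepant end" as a subcategory of dosing noncompliance. Taking more than one tablet on any day is a second subcategory of the same category.

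Protocol 6.5 requires study drug to be stopped for an exclusionary finding on the baseline laboratory report and asks subjects who discontinue for EOT procedures. Protocol Table 1 gives the EOT Visit no interval from the last dose. Protocol 4.3.2.1 allows the first dose on the day of the Baseline Visit or the day after.

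**The concern.** The reset shows that the SAP does not want subjects withdrawn for a baseline laboratory result to be charged for days after they were told to stop. Its trigger does not secure that. Whether such a subject is reset depends on the date of the last scheduled or EOT visit, which says nothing about how the drug was taken.

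Two related features affect the same row. Off-drug days after other protocol-directed stops lower the percentage once the count is 14 or more. And because tablets are not capped, a doubled day can make up for a missed one.

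This is a post-marketing required study of daily dosing, so readers will use the compliance and deviation tables to judge whether dosing really was daily. Some subjects who followed instructions may appear there as deviators, and some who dosed on fewer than 80% of days may be counted as 80% or more.

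**Working it through.** **Plan's own figure.** The SAP 9.2 example has records of 3 × 1, 4 × 1, 3 × 2 and 1 × 1 tablets, with the zero-tablet record excluded. Tablets = 3 + 4 + 6 + 1 = 14, and distinct dosing days = 10. Both match the SAP.

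**Rule as written.** Required = (later of last scheduled visit and last dose) − first dose + 1. If this is below 14, required = last dose − first dose + 1.

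**Reset.** Take a baseline-laboratory stop after 5 consecutive daily tablets. The visit days shown are those of the Week 2 window, "Week 2 (Day 14 +/- 2 days", that is, Days 12 to 16. They are an illustration, because an EOT Visit has no window of its own.

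| First dose | Last scheduled visit | Count | Reset to | Score |
|---|---|---|---|---|
| Day 1 | Day 12 | 12 | 5 | 100% |
| Day 1 | Day 13 | 13 | 5 | 100% |
| Day 1 | Day 14 | 14 | none | 5/14 = 35.7% |
| Day 1 | Day 15 | 15 | none | 5/15 = 33.3% |
| Day 1 | Day 16 | 16 | none | 5/16 = 31.3% |
| Day 2 | Day 14 | 13 | 5 | 100% |
| Day 2 | Day 15 | 14 | none | 5/14 = 35.7% |
| Day 2 | Day 16 | 15 | none | 5/15 = 33.3% |

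At a count of exactly 14, a subject with up to 11 daily tablets is flagged (11/14 = 78.6%) and one with 12 is not (12/14 = 85.7%). The reset does not excuse days missed before the last dose: 5 tablets spread over 10 days score 5/10 = 50%.

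**Other directed stops.** Suppose every tablet is taken for D days and the last scheduled visit is g days after the last dose. The score is D/(D + g), which is below 80% when g > D/4, provided D + g is 14 or more. The gaps below are assumed.

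- D = 28: g = 7 gives 28/35 = 80.0%, which passes; g = 8 gives 28/36 = 77.8%, which is flagged.
- D = 56: flagged from g = 15 (56/71 = 78.9%).
- D = 84: flagged from g = 22 (84/106 = 79.2%).

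The return visit 3 to 5 days after AST or ALT > 3x ULN (Protocol 8.4) is unscheduled, so it does not set maxdate. An interruption with restart often passes: 21 days off in 168 gives 147/168 = 87.5%.

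**Uncapped tablets.** 128 dosed days, 7 of them doubled, over 168 days: (128 + 7)/168 = 80.4%, against 128/168 = 76.2% of days dosed. In the SAP 9.2 example, with the count ending at the last dose, 14/13 = 107.7% against 10/13 = 76.9%.

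**What other outputs show.** Average exposure in SAP 6.2.6.1 is cumulative mg / days from first to last dose. The doubled-day subject shows 135 × 75/168 = 60.3 mg per day, below 75. The SAP 9.2 example shows 14 × 75/13 = 80.8 mg per day, above 75 although 3 of the 13 days had no dose. So the figure reflects missed days only net of doubling.

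**The case against.** The strongest reply is that the denominator is the protocol's own. Protocol 7.4 expects at least 80% to be consumed from Day 1 through the Treatment Phase, and Protocol 4.3.2 runs that phase to the Week 24 or EOT Visit. This stands. A reader might infer that the SAP contradicts the protocol by counting days after the last dose; it does not. For early discontinuations other than the baseline-laboratory group, the effect is a property of the measure. The reply does not cover the reset, which departs from that denominator for a stated purpose and then misses part of the group it names.

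A reader might also infer that missed days appear in no summary, or that doubling hides a deviation. Neither is supported. Average mg per day is summarised, and it is exactly 75 for a subject who took one tablet daily until a directed stop, whatever the EOT date. The by-subject listing gives dosing dates, "study day derived from study medication start date, and number of tablets taken per day". Any subject who reaches 80% of tablets on fewer than 80% of days must have more than one tablet recorded on some day, and so is flagged in the same SAP 9.1 category. What remains is that the subject still counts in the row for 80% or more, and that average exposure offsets missed days against doubled ones.

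Finally, the examples need a late last visit, and nothing in the documents suggests that long gaps are usual. That is fair. It limits the frequency, which is unknown, but not the inconsistency in the rule.

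**Conclusion.** The point holds and is minor. The reset does not do what SAP 6.2.6.2 says it is for: identical dosing scores 100% or 35.7% according to whether the required count is 13 or 14, and the lower score is listed as a deviation. The missing cap lets the tablet percentage exceed the percentage of days dosed, by 4.2 points in the 168-day example (80.4 − 76.2).

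The scores follow exactly from the written rule, but the visit dates and gaps are assumptions. The number of subjects affected cannot be estimated. SAP 5 raises expected non-completion from 27% to 40% because of baseline laboratory terminations, and 0.13 × 285 is about 37 subjects. A reader might take that as the number misclassified. It is a planning allowance for the whole difference, and those with a prompt EOT Visit are reset correctly.

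Nor do the documents support any effect on the main safety results. The safety analysis set needs only one dose, and no analysis set or primary endpoint uses compliance. Only the compliance table, its listing and the relevant-deviation outputs change.

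**What to change.** **(a) Extend the reset.** Keep the reset for counts below 14, and also apply it, whatever the count, when the recorded reason for not completing the OLT Phase is a baseline-laboratory exclusion. The disposition table in SAP 6.2.3.2 already reports "Reasons for not completing the OLT Phase, including not reported", but the documents do not say whether the CRF separates this reason, so that must be checked first. With the change, the 5-tablet subject seen on Day 14 scores 5/5 = 100%. The count trigger should not be replaced by the reason alone. A subject who stops for another reason after 5 daily tablets, with a visit on Day 13, would fall from 100% to 5/13 = 38.5% and be newly flagged, including some whose stop Protocol 6.5 requires.

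**(b) Add days dosed.** Add one row to the compliance table and one column to its listing: percentage of days dosed = dosing days / (study drug end date − study drug start date + 1). SAP 9.2 supplies the numerator: "A study drug dosing day is defined as a day on which" at least one tablet was taken, so each day counts once. Keep the tablet count and the flag for more than one tablet on a day beside it. The doubled-day subject would then show 76.2%, and a subject with 28 daily tablets followed by a directed stop would show 28/28 = 100%.

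**Cost.** One added condition, one row and one column; dosing days are already derived for the LFT plots. The new row does not show non-dosing after the last dose, which is why the tablet count stays.

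**Optional.** SAP 9.1 could show separately those below 80% only because of a documented protocol-directed stop. This needs subject-level review of AE and concomitant-medication data, because the dosing CRF fields described in SAP 6.2.6.1 hold no reason.
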